## 1. Background

### a. Value of communication skills

- i. The communication between clinicians and parents is a partnership; the family caregivers are equally important, as are their behaviors.
- ii. Especially important are parents' active behaviors, such as asking questions, introducing topics for discussion, expressing concerns, and sharing opinions.
- iii. Active patients receive more information and support from clinicians, are more satisfied with the care, and experience better outcomes than passive patients.

### b. Importance in the context of fetal anomalies

- i. Parents who have pregnancies diagnosed with a fetal anomaly are often overwhelmed by new medical information while they are in the process of grieving a normal pregnancy.
- ii. Often during this stressful time, medical decisions need to be made which are preference sensitive. Families and clinicians need to be able to work together to achieve a treatment plan that best fits a family's values.

### c. Proposed intervention

- i. We intend to address this problem by creating a short, animated Art of Medicine video delivered via text messages.
- ii. The goal of our educational intervention is to improve clinician-patient communication by equipping families with evidence-based skills that they can implement during medical encounters.
- iii. Our research team has developed a smartphone-based text-video educational platform with NIH support to prepare pregnant women for premature birth. We intend to use this platform to improve clinician-patient communication by disseminating concise, memorable, and immediately actionable education.

## 2. Aim:

- a. Determine the effect of the educational intervention on parents' communication during a fetal concerns appointment.

## 3. Study design

- a. The proposed intervention is to be implemented as randomized controlled study.

## 4. Study population

- a. A pregnant patient referred to Children's Wisconsin Fetal Concerns Center for a prenatal diagnosis.
- b. Own a smartphone
- c. 18 years of age or older
- d. Able to speak and understand English
  - i. Currently, the intervention is only available in English.

- e. Exclusion criteria:
  - i. Pregnant patient's appointment at Children's Wisconsin Fetal Concerns center is not for a fetal anomaly (e.g., screening only, past pregnancy with anomaly the only cause of appointment)
  - ii. Pregnant patient is considering termination of pregnancy.
- 5. Enrollment and consent
  - a. Upcoming Children's Wisconsin FCC appointment schedules will be screened by study team.
  - b. Eligibility will be discussed with a clinical team member (e.g., medical director [name], a nurse care coordinator). Prior to the first scheduled visit to the FCC clinic, the patient will be approached with a study introduction from the clinical team member through one or more of the following: encrypted email, phone call, or MyChart message. This introduction will assess patient interest in participation.
  - c. If interested, patients will be provided more study information and be invited to review an informational letter in REDCap. A waiver of documentation of consent is requested.
  - d. Participants will be invited to complete an enrollment questionnaire in REDCap prior to randomization and intervention delivery.
- 6. Randomization
  - a. Participants will be randomized 1:1 to receive either the video intervention or a control.
  - b. Randomization list will be generated by MCW Quantitative Health Sciences and will be implemented by study staff via REDCap.
- 7. Intervention & control
  - a. Intervention video development
    - i. We will develop the intervention's video objectives using published literature. Topics may include preparing questions for the appointment, summarizing using teach back, and participating in shared decision making.
    - ii. The video will be developed in a collaborative and iterative manner. After creating the script to meet the video's learning objectives, we will create the animation and audio using the software Vyond and Audacity, respectively. Professional voiceovers will provide narration and dialogue.
    - iii. The video will run approximately 10 minutes long and feature a diverse representation of families.
    - iv. This plan for creating and testing videos is similar to the procedure followed by [name] team, which successfully generated over 50 videos through user feedback.
  - b. Control education materials
    - i. Control education includes links to publicly available webpages from Children's Wisconsin describing the Fetal Concerns Center to

familiarize them with the clinic and prepare them for the appointment.

c. Education distribution plan:

- i. For participants randomized to the video intervention: After enrollment, participants will be registered to the Art of Medicine platform and be sent the video link by text message to their smartphone.
- ii. For participants randomized to the control: After enrollment, participants will be sent links to the Children's Wisconsin webpages by email or text message, depending on participant preference. After follow up assessment, control participants will also be sent the animated video.

8. Data collection

a. Medical record data

- i. After pregnant patients are enrolled, we will gather data from their medical records.
- ii. Data includes their date of birth, estimated due date, primary diagnosis / reason for referral, and obstetric history.

b. Website data

- i. Using tracking software already developed and utilized in [name] previous project, we will collect information regarding the number of video links sent, the number of links clicked, the number of complete and partial viewing of the video, and timestamps of views.

c. Questionnaires

- i. Participants will be asked to complete two questionnaires during the study, one at enrollment and one the day after their fetal concerns appointment.
- ii. The enrollment questionnaire will include a survey collecting information regarding sociodemographics, experience with healthcare providers, smartphone information, and a health literacy assessment (the HL6, see Supporting Documents).
- iii. The follow up assessment will include self-report items of participants describing their behavior before and during their appointment (see Supporting Documents).

9. Compensation

- a. For completing the follow up assessment, participants will receive \$20 in gift cards.

10. Data management

- a. All data will be stored securely at the Medical College of Wisconsin in REDCap. Only study team members will have access to identifiers.

11. Statistical analysis plan

- a. Missing data

- i. Logistic regression will be used to investigate the missing data pattern. In general, we will assume data are missing at random (MAR).
      - ii. We plan to use random effects models with maximum likelihood estimation for repeated measures and multiple imputations for items. We may miss obtaining some survey results or observe dropout for follow-up and will perform sensitivity analysis allowing for different assumptions.
    - b. Tracked video viewing data will be analyzed and correlated with study assessments and participant characteristics.
      - i. To examine relationships between assessment scores, participant characteristics, and tracked viewing data, we will use a generalized linear model, with link functions such as a negative binomial considered.
    - c. For patient participants, scoring of the follow up assessment will be calculated as percentage of communication behaviors self-reported as having occurred.
      - i. The primary outcome is a comparison of total follow up assessment scores in the video intervention group compared to the control.
      - ii. The analysis will include consideration of covariates, e.g., health literacy, income.
      - iii. Tracked video viewing data will be similarly analyzed.
12. Risks and benefits
- a. Potential risks
    - i. There is a minimal risk of mental distress while reviewing the video material or completing the questionnaires as reminders of a potentially distressing clinic appointment.
    - ii. There is a minimal risk of breach of confidentiality if (1) the security of data storage is violated, (2) the data is shared by people other than designated researchers and professionals, or (3) the result is reported in a manner that could reveal the identity of the participants.
    - iii. Physical risks or discomfort to the participants are minimal. No physical interventions are being undertaken.
  - b. Potential benefits
    - i. The potential benefits of the communication education for participants outweigh the minimal risks.
    - ii. This study will allow us to determine best methods of preparing parents to communicate during an appointment with complex medical information and shared decision making.

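### No pre-randomization measure of the patient's own communication activity is listed, so the single post-visit comparison gives up some precision, without being biased.

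*Combined protocol and SAP*

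**What the plan says.** Section 8.c.i sets two assessments: "Participants will be asked to complete two questionnaires during the study, one at enrollment and one the day after their fetal concerns appointment". Section 5.d places the first of them before allocation: "Participants will be invited to complete an enrollment questionnaire in REDCap prior to randomization and intervention delivery".

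The content of the first is given in 8.c.ii: "The enrollment questionnaire will include a survey collecting information regarding sociodemographics, experience with healthcare providers, smartphone information, and a health literacy assessment". The content of the second is in 8.c.iii: "The follow up assessment will include self-report items of participants describing their behavior before and during their appointment". Under 11.c, "scoring of the follow up assessment will be calculated as percentage of communication behaviors self-reported as having occurred", and 11.c.i makes the difference between arms in that total score the primary outcome.

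On adjustment, 11.c.ii says: "The analysis will include consideration of covariates, e.g., health literacy, income". These are examples, and the wording does not commit the analysis to any of them.

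Section 11.a.ii refers to random effects models for repeated measures, but no section describes an outcome that is measured more than once. That phrase is therefore not evidence of a baseline behaviour score.

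**The concern.** The outcome counts behaviours that a person reports about herself. Part of such a score plausibly reflects how active she usually is with clinicians and how she tends to answer items of this kind. The plan itself contrasts active with passive patients (1.a.iii) and names four active behaviours (1.a.ii). A baseline measure of that activity is the natural covariate for this outcome, and it is not among the listed data. Health literacy and income are less direct substitutes.

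Three things are at stake, all modest:

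- **Precision.** Between-person differences that could be explained stay in the residual.
- **Imbalance.** Without such a measure, a chance difference between arms in prior activity could be examined only through indirect variables.
- **Missing scores.** Section 11.a assumes data are missing at random. A plausible predictor of the score would help the imputation model.

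The timing is favourable, because the enrollment questionnaire already precedes randomization. The population also makes the question answerable. Section 4.a requires "A pregnant patient referred to Children's Wisconsin Fetal Concerns Center for a prenatal diagnosis", so a recent prenatal visit to report on can reasonably be expected. Once a participant has been randomized, a true baseline can no longer be collected from her.

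**Working it through.** **Inputs from the documents.** 1:1 allocation (6.a); one follow-up score per participant (8.c, 11.c); enrollment data taken before randomization (5.d). No sample size, alpha, power, effect size, standard deviation or correlation is stated, so there is no figure of the plan to reproduce.

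**Step 1: gain from one baseline covariate.** Let r be its partial correlation with the follow-up score, given the covariates already in the model. Residual variance is multiplied by 1 − r², and the equivalent sample-size factor is 1/(1 − r²). The values of r are assumed.

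| r | 1 − r² | variance reduction | 1/(1 − r²) |
|---|---|---|---|
| 0.2 | 0.96 | 4% | 1.04 |
| 0.3 | 0.91 | 9% | 1.10 |
| 0.4 | 0.84 | 16% | 1.19 |
| 0.5 | 0.75 | 25% | 1.33 |

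**Step 2: what that means for power.** Illustration only, with assumed inputs: standardized difference 0.5, two-sided alpha 0.05, 80% power. This needs 63 per arm unadjusted (power 80.1%).

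| r | n per arm for 80% power | power at 63 per arm |
|---|---|---|
| 0.2 | 61 | 81.7% |
| 0.3 | 58 | 83.7% |
| 0.4 | 53 | 86.5% |
| 0.5 | 48 | 90.0% |

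**Step 3: can a short scale reach such an r?** For four items with mean inter-item correlation c, reliability is 4c/(1 + 3c). With c assumed between 0.15 and 0.50, this is 0.60/1.45 = 0.41 to 2.00/2.50 = 0.80. If the underlying trait correlates 0.5 with the follow-up score (assumed), the observed r is 0.5 × √0.41 = 0.32 to 0.5 × √0.80 = 0.45. The variance reduction is then about 10% to 20%, inside the range of Step 1. This step makes no allowance for overlap with other covariates.

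**Step 4: cost of estimating one more coefficient.** With n per arm, the variance factor becomes approximately (1 − r²)(2n − 4)/(2n − 5). At n = 20 (assumed), r = 0.2 gives 0.96 × 36/35 = 0.987 and r = 0.5 gives 0.75 × 36/35 = 0.771. In a small trial the gain at r = 0.2 almost disappears.

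**Step 5: break-even for prompting.** Power depends on effect divided by standard deviation, so a proportional shrinkage of the effect by 1 − √(1 − r²) would cancel the gain: about 2% at r = 0.2, 5% at r = 0.3 and 13% at r = 0.5.

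**The case against.** The strongest objection is that the provider-experience part of the enrollment survey is not shown. It may already record the patient's own behaviour or a close proxy. This stands: what is established is the absence of a listed measure. If those items are suitable, the point reduces to naming them as a covariate, which 11.c.ii does not do.

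The size is also open to challenge, and this stands too. The correlation is assumed. A baseline could only concern a different visit, because patients are approached before their first visit to this clinic (5.b). It should leave out the skills taught in the video, although the outcome may include them. Only the increment over health literacy, income and similar variables counts. A reader might take a correlation of 0.6 and expect 36% less variance, but nothing in the documents supports so high a value for a short proxy.

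Asking about these behaviours may prompt them, and Step 5 shows that a modest shrinkage would cancel the gain. This stands only in part. Both arms are asked the same items before allocation, so the contrast shrinks only if the prompt overlaps with what the video does or pushes scores towards a ceiling. Leaving out the taught skills limits that overlap.

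Section 12.a.i already names questionnaires as a possible source of mental distress. Questions about a recent prenatal visit could touch on it, which is a reason to keep the set short.

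A reader might also infer that prior activity is the variable most likely to predict a missing score, so that the missing-data plan fails without it. The documents do not show this. Section 11.a already provides for modelling of missingness, multiple imputation and sensitivity analyses.

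**Conclusion.** The point holds as one of precision. No pre-randomization measure of communication activity is listed, the outcome is a single post-visit score, and the means to collect a baseline before allocation already exist.

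For an assumed partial correlation of 0.2 to 0.5 beyond the other covariates, residual variance would fall by about 4% to 25%, equivalent to 1.04 to 1.33 times as many participants. At 0.2 or below the gain is negligible.

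A reader might infer that the lack of a baseline biases the comparison, or that the design is invalid. Neither follows: a post-only comparison between randomized arms is legitimate. Nor can it be shown that the trial needs the extra precision, since no sample size is stated. For the same reason, nothing shows that precision is ample. The change is worth making because it is cheap and cannot be made for participants already randomized.

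**What to change.** 1. Check the provider-experience items in the enrollment survey. If they record the patient's own communication behaviour, prespecify that score as a fixed covariate in the primary model of 11.c and as a predictor in the imputation model of 11.a.
2. If they do not, add a short set of items to the enrollment questionnaire (5.d, 8.c.ii), answered before randomization. Ask how much, at a recent prenatal visit, she put questions, raised topics herself, voiced worries and gave her views. These are the four behaviours in 1.a.ii. Do not name skills taught in the video, such as teach back or preparing questions. Use the summed score as in step 1.

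Cost: about a minute of extra questions per participant, a few REDCap fields and one sentence in section 11. The downside is possible prompting in both arms. This cannot bias the comparison but could slightly shrink the effect.
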